7.4 Procedural Exclusion Criteria

Subjects are considered procedural screen failures if the investigator is unsuccessful at placing the OTX-DED or HV intracanalicular ophthalmic insert in both eyes (i.e. neither eye has an insert). Subjects will be followed per protocol if the investigator successfully places one insert.

7.5 Subject Recruitment and Screening

Each subject that is screened will be assigned a Subject Identification (ID) consisting of a 2-digit Site number plus a 3-digit Subject number. The Subject ID will be used as the primary subject identifier for the duration of the study. Once all inclusion and exclusion criteria are met at Visits 1 and 2, each qualifying subject will be randomized via the IRT system and will be assigned a randomization number.

The subject must sign the Informed Consent Form (ICF) before his or her participation in the study. A copy of the ICF must be provided to the subject or the subject's legal guardian. If applicable, it will be provided in a certified translation of the subject's first or native language. The original signed ICF for

each participating subject shall be filed with records kept by the investigator and must be available for verification by study monitors at any time, and a copy will be given to each subject.

7.6 Withdrawal Criteria

Any subject who wishes to voluntarily discontinue study drug or withdraw from participation in the study for any reason is entitled to do so without obligation.

IP may be discontinued (insert removed [see [Appendix 13](#)]) and any subject may be discontinued from study participation at any time during the study at the discretion of the Investigator or the Sponsor for any reason.

7.6.1 Withdrawal Methods

The Sponsor may terminate this study at any time. Reasons for termination may include but are not limited to, the following:

- The incidence or severity of adverse events (AE) in this or other studies point to a potential health hazard for trial subjects.
- Insufficient subject enrollment.
- Any information becoming available during the study that substantially changes the expected benefit risk profile of the study treatments.

7.6.2 Collection of Data from Withdrawn Subjects

In the event that study discontinuation of a randomized subject is necessary, the Investigator should make every attempt to have the subject complete Visit 7 assessments as soon as possible. The reason for premature discontinuation should be recorded in the subject chart and entered in the eCRF.

7.6.3 Subject Replacement

Subjects who withdraw will not be replaced.

8 SUBJECT TREATMENT

8.1 Treatment Regimen

OTX-DED contains 0.2 mg or 0.3mg of micronized dexamethasone in a resorbable hydrogel matrix. It is intended to be inserted at Visit 2 and retained in the inferior or superior vertical canaliculus where it then provides sustained release of therapeutic levels of dexamethasone over approximately 14 - 21 days.

8.2 Prior and Concomitant Therapy

Only sponsor provided preservative free artificial tear use will be permitted as rescue therapy during the study. All other tear substitutes are not permitted.

Table 3 List of Prohibited/Restricted Medications

Minimum Washout Period Prior to Screening (Visit 1)	
30 days:	
Topical ocular cyclosporine (e.g., Cequa [®] , Restasis [®])	
Lifitegrast (Xiidra [®])	
Autologous tears	
Topical ocular corticosteroids	
Topical ocular antibiotics	
Topical ocular NSAID	
Topical ocular antihistamines and/or mast cell stabilizers	
Topical ocular or nasal vasoconstrictors	
Intranasal Tear Neurostimulation	
Stable within 30 days of Visit 1 and stable throughout study:	
Nutraceuticals or multivitamins	
Tetracycline compounds (tetracycline, doxycycline or minocycline)	
Inhaled, intramuscular or intra-articular corticosteroids (mouth or nasal spray form)	
Stable within 6 months of Visit 1 and stable throughout study:	
Systemic anticholinergics	
Antidepressants (with the exception of rare usage as a sleep aid)	
Oral corticosteroids (e.g., prednisone, prednisone dose must be less than 11mg/day)	
90 days:	
Periocular injection of any corticosteroid	
Corticosteroid intra-vitreal depot injection	
6 months:	
Ozurdex	
Isotretinoin	
Systemic Immunosuppressants	
40 months:	
Retisert	

8.3 Rescue Therapy

Use of preservative-free artificial tears (AT) should be discouraged, and subjects should be counseled to administer only if absolutely necessary as rescue. Further, if used, subjects will be instructed not to administer AT within 2 hours prior to any study visit. Preservative-free AT will be provided by the sponsor and use will be recorded by subjects in a daily diary.

8.4 Study Assessments by Visit

Perform study procedures as referenced in the Schedule of Events ([Appendix 1](#)) in the order specified below. Note: All subjects will have both eyes evaluated at all visits.

8.4.1 Visit 1 (14 ±2 days prior to Day 1) Screening/Baseline Visit

Note: The Screening Visit can be split into two (2) visits in rare cases, but both visits must be within the allowable window.

- Informed consent
- Demographics
- Medical/ophthalmic history
- Record concomitant medications
- VAS Severity and Frequency for Eye Dryness ([Appendix 2](#))
- OSDI ([Appendix 3](#))

- SPEED assessment ([Appendix 4](#))
- BCVA assessment ([Appendix 8](#))
- Slit lamp biomicroscopy (including punctum assessment) ([Appendix 9](#))
- Investigator Rated Assessment of Bulbar Conjunctival Hyperemia ([Appendix 5](#))
- CFS ([Appendix 7](#))
Note: Wait 15 minutes prior to conducting unanesthetized Schirmer test
- Unanesthetized Schirmer
- IOP
- Dilated fundus exam
- Determine Eligibility
- Dispense artificial tears (as needed and not to be administered within 2 hours of clinic visit.)
- Dispense Daily Subject Diary for Artificial Tear Use (as needed) ([Appendix 14](#))

8.4.2 Visit 2 Insertion/Day 1

- Record concomitant medications
- Record AEs*
Note: Any signs, symptoms or conditions captured prior to the insertion of IP, will be recorded as medical history.
- Collect and review Subject Daily Diary for Artificial Tear Use (if applicable)
Note: Subjects using rescue AT > 3x/day for 3 consecutive days will be ineligible for randomization.
- VAS Frequency and Severity for Eye Dryness
- OSDI
- SPEED assessment
- Conjunctival Hyperemia Photography ([Appendix 6](#))
- BCVA assessment
- Slit lamp biomicroscopy, including punctum evaluation
- Investigator Rated Assessment of Bulbar Conjunctival Hyperemia
- CFS
- IOP
- Punctum Size Assessment
- Urine pregnancy test (if applicable must be performed prior to treatment)
- Determine Eligibility for Insertion
- Randomization
- OTX-DED or HV Insert Placement ([Appendix 11](#))*

Note: If placement is only successful in one eye, the items with the asterisk should be performed on the same day. Subjects should be asked to return within 0-3 days to attempt insertion in the other eye. At the return visit, items with an asterisk should be performed on the second eye, and the AE review, Ease of Insertion Assessment and Tear film PK for the second eye should only be performed if the second eye has a successful insertion.

- Ease of Insertion Assessment*
- Tear film PK by Schirmer (to be collected 1 hour (\pm 30 minutes), 2 hours (\pm 30 minutes) and 4 hours (\pm 30 minutes) post-insertion)* ([Appendix 10](#))
- Dispense artificial tears (as needed and if used, not to be administered within 2 hours of the clinic visits)
- Dispense Daily Subject Diary for Artificial Tear Use (as needed)

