9 ADVERSE EVENTS

The investigator and study staff are responsible for detecting and recording AEs and SAEs, during scheduled safety evaluations and whenever such information is brought to their attention.

This section of the protocol provides definitions and detailed procedures to be followed.

During each visit, the Investigator will question the subject about adverse events using an open question taking care not to influence the subject's answers. Throughout the course of the study, every effort must be made to remain alert to possible AEs. If an AE occurs, the first concern should be for the safety of the subject. If necessary, appropriate medical intervention should be provided. At the signing of the ICF, each subject must be given the names and telephone numbers of study site staff for reporting AEs and medical emergencies.

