Appendix 1 Time and Events Schedule

See [Section 8.4](#) for order of assessments.

Study Parameter	Screening/ Baseline Visit Day -14 (-16 to -12)	Insertion Day 1	Follow-up Day 8 Week 1 ±2 days	Follow-up Day 15 Week 2 ±2 days	Follow-up Day 22 Week 3 ±2 days	Follow-up Day 29 Week 4 ⁶ ±3 days	Follow-Up Day 57 Week 8 (± 10 days)
Visit	1	2	3	4	5	6	7
Informed Consent	X						
Determine Eligibility	X	X					
Demographic Information	X						
Medical/Ophthalmic History	X						
Record Medications	X	X	X	X	X	X	X
Record Adverse Events ^{3,7}		X	X	X	X	X	X
Urine Pregnancy Test ¹		X					X
VAS for Eye Dryness	X	X	X	X	X	X	X
OSDI	X	X	X	X	X	X	X
SPEED	X	X	X	X	X	X	X
Conjunctival Hyperemia photography		X		X			
Assessment of BCVA	X	X	X	X	X	X	X
Slit Lamp Biomicroscopy (including punctum assessment)	X	X	X	X	X	X	X
Investigator Rated Conjunctival Hyperemia grade	X	X	X	X	X	X	X
Corneal Fluorescein Staining Using the NEI Scale	X	X	X	X	X	X	X
OTX-DED or HV Insert Presence by Visual Assessment			X	X	X	X	X
Ease of Visualization as assessed by Investigator			X	X	X	X	X
Unanesthetized Schirmer Tear Test	X						
Tear Film PK performed using Schirmer Strips ^{3,4,5}		X	X	X	X	X	X
IOP Measurement	X	X	X	X	X	X	X
Fundus Exam ²	X						X
Punctum Size Assessment		X					X
Randomization		X					
OTX-DED or HV Insert Placement ³		X					
Ease of Insertion as assessed by the Investigator ³		X					
Dispense Sponsor Supplied Artificial Tears (if needed) and Daily Diary	X	X	X	X	X	X	
Collect/review Daily Subject Diary for Artificial Tear Use (as needed)		X	X	X	X	X	X

¹ A negative UPT is required for women of childbearing age to be included in the study.

- 2 Dilated fundus examination at screening; undilated fundus examination at Week 8.
- 3 Prior to insertion, a clinical determination of the absence of infection will be made based on the lack of erythema or discharge at the punctum. If placement is only successful in one eye, subjects should be asked to return within 1-3 days to attempt insertion in the other eye. The following items should be repeated at the return visit, Insert Placement, Ease of Insertion, Tear Film PK and AEs.
- 4 Tear Film PK will be collected at 1 hour (± 30 minutes), 2 hours (± 30 minutes), and 4 hours (± 30 minutes) post insertion on Day 1. Tear Film PK should be collected using Schirmer strips.
- 5 Tear Film PK will be collected using Schirmer Tests strips. These will be collected and sent to the central lab for analysis. See lab manual.

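### Section 8.4.2 lists the Day 1 adverse-event item before insert placement with none after it, and conflicts with Appendix 1 on adverse-event review after a failed second attempt

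*Protocol*

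**What the plan says.** Protocol Section 8.4 tells sites to carry out the procedures "in the order specified below". In the Visit 2 list (Section 8.4.2), AE recording is the second item and carries an asterisk. The questionnaires, photography, examinations, eligibility check, randomization and insert placement come after it. Below placement the list has only the ease-of-insertion grade, tear film PK at 1, 2 and 4 hours (each ±30 minutes), and dispensing of tears and diary. The note under the AE item reads "Note: Any signs, symptoms or conditions captured prior to the insertion of IP, will be recorded as medical history".

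A second note deals with one-eye success: "If placement is only successful in one eye, the items with the asterisk should be performed on the same day". It continues: "Subjects should be asked to return within 0-3 days to attempt insertion in the other eye". It then says that the AE review, ease-of-insertion grade and PK for the second eye "should only be performed if the second eye has a successful insertion".

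Appendix 1 footnote 3, repeated under the SAP schedule of assessments (SAP Section 2.5), gives a return interval of 1-3 days and states: "The following items should be repeated at the return visit, Insert Placement, Ease of Insertion, Tear Film PK and AEs". It sets no success condition. Footnote 7, attached to the AE row of the same table, sends findings that arise before the Day 1 insertion to medical history.

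Section 9 adds a general rule: "During each visit, the Investigator will question the subject about adverse events using an open question". Section 9.4.1 requires any AE from Visit 2 through Visit 7 to be entered in the eCRF. SAP Section 4.4 has subjects with failed placement in both eyes leave the study at that point.

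**The concern.** AEs are the primary safety evaluation (protocol Section 6.2.3), and obtaining safety information is one of the reasons given for the sample size (Section 10.3). Section 4.4 lists risks already seen with the insertion procedure, among them eye pain, foreign-body sensation, tearing, and trauma to or perforation of the punctum. Some of these can be brief. A question asked before placement cannot find them, and a question asked a week later may miss those that have resolved.

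The return-visit wording adds a second gap. A failed second attempt is still an attempt that can injure the punctum, yet under Section 8.4.2 it is the one case in which the second-eye AE review is expressly left out. A site cannot follow both that note and Appendix 1 footnote 3. What is at stake is the credibility of the absolute rate of procedure-related events.

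**Working it through.** The documents state no figure for this point, so there is none to reproduce. The check sets the passages side by side and follows each type of subject through them. The only arithmetic is on visit timing.

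**Timing inputs**
- Last Day 1 contact: the 4-hour PK sample, ±30 minutes, so 3.5 to 4.5 hours after insertion (Section 8.4.2).
- Visit 3: Day 8 ±2 = Day 6 to Day 10 (Section 8.4.3, Appendix 1). Counted from Day 1: 6 − 1 = 5 to 10 − 1 = 9 days after insertion.
- Return visit: 0-3 days after Day 1 = Day 1 to Day 4 (Section 8.4.2), or 1-3 days = Day 2 to Day 4 (Appendix 1 footnote 3).
- From return visit to Visit 3: under Section 8.4.2, 6 − 4 = 2 to 10 − 1 = 9 days; under Appendix 1, 6 − 4 = 2 to 10 − 2 = 8 days.

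**What is listed for each type of subject**
1. *Both eyes placed on Day 1.* If the list is followed literally, no AE item comes after placement until Visit 3, 5 to 9 days later. The subject is on site for PK sampling for about 4 hours after placement.
2. *One eye placed on Day 1.* The asterisk note calls for AE recording the same day, once the one-eye result is known.
3. *Second eye placed at the return visit.* Both texts call for an AE review then. They differ only on the interval.
4. *Second attempt fails at the return visit.* Section 8.4.2 omits the second-eye AE review; Appendix 1 footnote 3 and the SAP footnote repeat it. The subject holds one insert, is followed per protocol (Section 7.4), is in the Safety population (SAP Section 3.1), and is next asked at Visit 3, 2 to 9 days later.
5. *Neither eye placed.* The subject exits (SAP Section 4.4). No AE item is listed after the attempt, and there is no Visit 3. SAP Section 4.4 counts these subjects as randomized but not treated, so their events would fall outside the Safety-population tables, but they should still be collected and listed.

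**Content against position**
The medical-history note and footnote 7 both remove pre-insertion findings from the AE record. What remains for the Day 1 AE entry is post-insertion events. The intended content therefore requires a question after placement, while the binding order puts the item before it. Section 9 does not settle this: a question asked as the second item of Visit 2 meets the rule of asking at each visit.

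**The case against.** The best defence is that the documents show what was meant. The asterisk groups AE recording with placement, ease of insertion and PK. The return-visit note makes the AE review depend on whether insertion succeeded, which is possible only if the review follows placement. With the medical-history note and footnote 7, this suggests that the item's place in the list is a drafting slip. Section 9 requires the AE question at each visit, and Section 9.4.1 requires recording from Visit 2 on. The Section 8.4.2 restriction is worded for the second eye and is contradicted by footnote 3, so it is not a settled rule. The listed order is the same in every arm, and no bias against vehicle is shown.

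Most of this stands. A reader might infer that nobody is asked about AEs until around Day 8, or that the Day 1 entry can never hold a treatment-emergent event. The documents do not support either reading. Section 9 applies to Visit 2 and to the return visit, one-eye successes have a same-day rule, a successful second insertion brings its own review, and subjects whose second attempt fails are still asked at Visit 3. Nor is it a defect that the Day 1 slit lamp, acuity and pressure measurements precede insertion: they serve as baseline and eligibility measures, and Section 8.4.8 allows unscheduled safety examinations.

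What the defence leaves open is the wording. Intent inferred from footnotes does not tell a site when to ask, the order is declared binding, and one sentence expressly omits a review after a failed attempt.

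**Conclusion.** The point holds as an ordering fault and an internal conflict. The timing of the AE question within Day 1 is not stated, and its listed position contradicts its intended content. Section 8.4.2 conflicts with Appendix 1 footnote 3 and the SAP schedule on AE review after a failed second attempt and on the return interval. Subjects with failed placement in both eyes have no listed query after the attempt.

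The likely effect is some under-recording of short-lived procedure events in all arms, which mainly lowers absolute procedure-event rates. Its size cannot be derived from the documents: that would need the frequency of transient insertion-day events, the share still reported 5 to 9 days later, and the share caught on Day 1 under Section 9 or by spontaneous report. None of these is given. The conclusion assumes that at least some sites follow the list as written and that some procedure events resolve before Visit 3. The correction is worth making because it is cheap and concerns the primary safety evaluation.

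**What to change.** - In Section 8.4.2, list the Day 1 AE question after insert placement, for example at the end of the tear PK collection. Keep the medical-history note for findings made before insertion.
- Reconcile the return-visit note with Appendix 1 footnote 3 and the SAP schedule, so that AEs are reviewed after every insertion attempt, successful or not. Include a review before the exit of subjects with failed placement in both eyes.
- Reconcile the return interval (0-3 against 1-3 days) across Section 8.4.2, Appendix 1 and the SAP schedule.

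The cost is a wording change in the protocol and site worksheet, a matching check of the SAP table, and a few minutes of site time per attempt. Subjects with an insert placed are already on site for PK sampling, so no visit or procedure is added.

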Appendix 11 OTX-DED or HV Insert Suggested Placement Technique

The following is the suggested placement technique and it can be modified based on investigator's medical judgment.

[figure not shown]
1. Apply lateral pressure to elongate the canalicular system. Pull the skin near the punctum down and temporally. A technician may assist if needed.

[figure not shown]
2. Dilate using the punctal dilator in towards the nose, ensuring the system is elongated. Dilate through the punctum deeper into the canaliculus, dilate for depth, as well as width. If desired, rotating the dilator in a spinning motion may help with the dilating process.

3. Dry the surface around the punctal opening using an ophthalmic sponge. More than one sponge may be necessary to ensure adequate drying of area. A technician may assist if needed.

[figure not shown]
4. Grasp OTX-DED or HV insert with forceps and insert at a slight angle towards the nose. Aim for 70% of insertion within the first motion. Use forceps to tap or push insert the remainder of the way in. The insert should sit slightly beneath the punctal opening.

Note: Excessive squeezing of OTX-DED or HV may cause deformation. The product should be handled with care, so it maintains its original shape prior to insertion. If the insert hydrates before placement slightly below the punctal opening (resembling a trumpet shape), it should be discarded and a new insert should be used. If the insert hydrates before ideal positioning or if a portion of the insert is protruding and unable to be inserted, it should be removed, discarded and a new insert should be used. (Note: cutting of the exposed insert is NOT allowed.)

5. OTX-DED or HV insert can be visualized when illuminated by a blue light source (e.g., slit lamp or hand-held blue light) with yellow filter.

Placement of OTX-DED or HV insert in Canaliculus

The investigator will grade the level of ease of insertion of the ophthalmic insert as “easy” (1), “moderate” (2) or “difficult” (3).

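### Section 8.4.2 drops the second-eye adverse-event review after a failed re-insertion, contrary to Appendix 1 footnote 3 and Section 9

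*Protocol*

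**What the plan says.** Under Protocol Section 7.4, a subject with an insert in one eye stays in the study: "Subjects will be followed per protocol if the investigator successfully places one insert". The note in Section 8.4.2 asks such a subject to come back within 0-3 days for an attempt on the other eye. It says the asterisked items, which include the recording of AEs, are to be done on the second eye. The same sentence then limits three of them to the case of a successful placement: "AE review, Ease of Insertion Assessment and Tear film PK for the second eye should only be performed if the second eye has a successful".

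Other parts of the plan say otherwise:

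- Appendix 1, footnote 3: "The following items should be repeated at the return visit, Insert Placement, Ease of Insertion, Tear Film PK and AEs". No success condition is attached. SAP Table 2 carries the same footnote. Both give the return window as 1-3 days.
- Section 9: "During each visit, the Investigator will question the subject about adverse events using an open question". Staff must also record events "whenever such information is brought to their attention".
- Section 8.4, introductory note: "All subjects will have both eyes evaluated at all visits". The same section refers sites to Appendix 1.
- Section 9.4.1: every AE from Visit 2 to Visit 7 goes into the eCRF.

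**The concern.** The condition removes the prompt from the eyes where a procedural event is a real possibility. A failed attempt is still a procedure. Step 2 of the placement technique in Appendix 11 reads "Dilate through the punctum deeper into the canaliculus, dilate for depth, as well as width", and it comes before the insert is picked up. Section 4.4 lists pain, tearing and punctal trauma among the risks of the insertion procedure, and none of these needs a retained insert.

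Such events belong in the safety analysis. The subject already has an insert in the first eye, so is in the Safety population. Anything starting after that insertion is treatment-emergent under SAP Section 4.9.1. Section 9.7.2 judges relatedness partly on timing relative to the insertion procedure, so a late report makes that call less certain. With two conflicting instructions, sites may also follow different ones, and ascertainment would then be uneven.

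**Working it through.** The plan states no figure to reproduce. The check has two parts: whether the texts conflict, and how long the prompt is delayed if a site follows 8.4.2.

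**Texts side by side, for a return visit at which the second insertion fails**

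| Source | AE review at the return visit? |
|---|---|
| Protocol 8.4.2, first half of the sentence (asterisked items) | Yes, for the second eye |
| Protocol 8.4.2, second half of the sentence | No, for the second eye |
| Appendix 1 footnote 3 and SAP Table 2 footnote 3 | Yes, no condition |
| Protocol Section 9 | Yes, open question at each visit |

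SAP Section 4.7.4 names a Visit 2B for the ease-of-insertion data, which supports counting the return as a visit under Section 9. The specific restriction in 8.4.2 is the only text against asking, but it is explicit, and the documents give no rule on which text takes precedence.

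**Delay to the next scheduled AE question**

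Inputs:

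- Day 1 is the first attempt (Section 8.4.2).
- Return offset is 0-3 days (Section 8.4.2) or 1-3 days (Appendix 1 footnote 3).
- Visit 3 is Day 8 ± 2 days, so Day 6 to Day 10 (Section 8.4.3 and Appendix 1).

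Formulas: return day = 1 + offset; gap = Visit 3 day − return day.

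| Return window | Return days | Gap, Visit 3 on Day 8 | Gap, Visit 3 on Day 6 to 10 |
|---|---|---|---|
| 0-3 days | 1 to 4 | 8 − 4 = 4 to 8 − 1 = 7 | 6 − 4 = 2 to 10 − 1 = 9 |
| 1-3 days | 2 to 4 | 8 − 4 = 4 to 8 − 2 = 6 | 6 − 4 = 2 to 10 − 2 = 8 |

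The 7-day and 9-day ends need a re-attempt on Day 1 itself, which only 8.4.2 allows. If AEs are reviewed after every attempt, the delay to the prompted question is 0 days.

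For scale, the ordinary wait from Day 1 to Visit 3 for any subject is 8 − 1 = 7 days, or 6 − 1 = 5 to 10 − 1 = 9 days with the window.

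**Number of subjects affected.** This would be the number whose second eye fails on Day 1 and again at the return visit. The documents give no insertion failure rate, so it cannot be computed.

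**The other two restricted items.** Tear film PK from an eye without an insert has no purpose here. For the ease grade, Appendix 11 says "The investigator will grade the level of ease of insertion of the ophthalmic insert as" easy, moderate or difficult, with no level for failure. Making these two conditional on success is reasonable.

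**The case against.** The case on the other side is that little is lost in practice.

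- The 8.4.2 sentence contradicts itself, since the recording of AEs carries the asterisk, and Section 8.4, Appendix 1 and Section 9 all favour asking.
- Section 9 prescribes one open question to the subject, not one per eye. The subject has an insert in the first eye and is at a visit, so the question is due anyway and the answer can cover either eye.
- The investigator performs the attempt and would see immediate pain or trauma. Volunteered or noticed events must be recorded. Subjects hold site telephone numbers, and unscheduled visits can include AE assessment.
- The gap is no longer than the normal interval from Day 1 to Visit 3, and events starting after the subject leaves would wait for Visit 3 even under the fix.
- The 7-day end also needs the Day 1 AE record to have been taken before a same-day re-attempt.

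All of this stands as a limit on the harm. Visit 3 also repeats the AE question, with slit lamp and punctum assessment, so lasting injury should be found. None of it removes the conflict. The asterisk does not settle it, because the same sentence goes on to take the AE review out. A coordinator working from the visit procedure can reasonably treat a specific restriction as overriding a general rule.

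**Conclusion.** The point holds. Section 8.4.2, as written, withholds the second-eye AE review after a failed re-attempt, against Appendix 1 footnote 3, its SAP copy and Section 9. If a site follows it and asks no question covering that eye, the next scheduled prompt comes 4 to 7 days later with Visit 3 on Day 8 (4 to 6 days under the 1-3 day return window). Across the Visit 3 window the range is 2 to 9 days (2 to 8 days).

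What is at risk is a short-lived procedural event reported late, with a less certain onset, or missed. The affected group is probably small and cannot be counted from the documents. No efficacy endpoint and no sample-size consideration is touched. The change should be made because it concerns safety collection and costs almost nothing; the conflict does not threaten the trial's conclusions.

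**What to change.** Replace the last clause of the 8.4.2 note with:

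*At the return visit, the AE review is performed after any attempt on the second eye, successful or not; the Ease of Insertion Assessment and Tear film PK for the second eye are performed only if the insertion succeeds.*

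Put the same conditions in footnote 3 of Appendix 1 and in its copy in SAP Table 2. As an editorial correction, give one return window, 0-3 or 1-3 days, in all three places.

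The cost is one clause and one aligned footnote in two tables. For sites it means a few minutes of AE questioning at a visit that already takes place.
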